Study Title: 4DCT Imaging for Improved Diagnosis and Treatment of Wrist Ligament Injuries

NCT#: NCT03193996

Document Date: 13 September 2022

General Study Information

Principal Investigator: [name]

Study Title: 4DCT Imaging for improved diagnosis and treatment of wrist ligament injuries

Protocol version number and date: 5.0, 09/13/2022

Research Question and Aims

Specific Aim #1: Establish the relationship between SLIL injury and 4DCT metrics in vitro. Cadaveric specimens will be scanned using our 4DCT approach and location of scapholunate gapping determined during simulated wrist movements, following the intact condition and each of the sequential cuts to the palmar, membranous, dorsal SLIL, and secondary ligament stabilizers. The scientific premise for this aim is our pilot cadaveric and patient imaging¹⁷ using 4DCT, as well as supporting literature^{2, 22-29}.

Hypothesis 1: The size and location of gapping (palmar or dorsal) at the scapholunate joint during wrist motion is related to location of ligament injury.

Specific Aim #2: Assess the location of SLIL injury in patients using 4DCT metrics. Patients with unilateral SLIL injury will be scanned pre-surgically using 4DCT during wrist movement to characterize scapholunate gapping and predict injury location. Patients will have arthroscopic confirmation of location of ligament injury. The scientific premise for this aim is our pilot work that established a relationship between unilateral SLIL injury and 4DCT metrics¹⁷.

Hypothesis 2: The location of ligament injury can be predicted by the size and location of palmar or dorsal gapping at the scapholunate joint.

Specific Aim #3: Determine the effect of targeted treatment of SLIL injury on post-surgical outcomes, as assessed using 4DCT metrics. Surgeons will assess scapholunate gapping and document a treatment plan to address the specific injury. Then, 4DCT imaging findings will be compared with arthroscopic evaluation. 4DCT will also be performed at 1 year postoperatively, and radioscapoid contact patterns will be assessed during wrist movement to determine if normal patterns of motion are restored. The scientific premise for this aim is reports of unsuccessful treatment resulting in OA at the radioscapoid joint^{5-9, 20}.

Hypothesis 3a: Pre-operative treatment planning using 4DCT will provide equivalent findings as arthroscopic observations.

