**Table 1. In vitro testing conditions.**

All ligaments intact (15M, 15F)
Volar SLIL cut
Membranous SLIL cut
Dorsal SLIL cut
Radioscaphocapitate cut
Long radiolunate cut

or flexion-extension motion at 30 deg/sec which simulates in vivo wrist motion speeds. A motion cycle is approximately 2 seconds. The wrist will be cycled 100 times in flexion-extension prior to each testing condition. A static CT image will be acquired in the neutral posture. Then, each wrist will be imaged using 4DCT during flexion-extension and radial-ulnar deviation, in the following conditions: intact (control), volar SLIL cut, membranous SLIL cut, dorsal SLIL cut, radioscapheocapitate ligament cut, and long radiolunate ligament cut (**Table 1**).

Aim 2:

4DCT scanning will be performed bilaterally on 60 patients (30 males, 30 females) with unilateral SLIL injury who are scheduled to undergo a surgical intervention. In addition, patients will have pre-surgical volar and dorsal arthroscopic confirmation of ligament injury, categorized by Geissler and European Wrist Arthroscopy Society (EWAS) classifications; video recording of the arthroscopy will be obtained for later analysis. PRWE and VAS questionnaires will be completed at the 4DCT visit for the injured wrist and the Total PRWE Score (sum of pain and function subscales) and composite change in VAS score used in the analysis. 4DCT wrist data will be obtained while the subjects perform flexion-extension and radial-ulnar deviation. The dynamic image sequence will be processed with existing software tools to obtain metrics describing the interosseous distances between the articular surfaces of the scaphoid, lunate, and radius, during the movement cycles. Given the difficulty of diagnosing SLIL injury, the uninjured contralateral wrist is often used as a “control” for comparison by physicians; therefore, the difference in right/left metrics will be used in the study.

Aim 3:

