The same 60 patients (see Aim 2) will be evaluated. Surgeons will assess pre-surgical scapholunate interosseous distances (quantified using 4DCT in Aim 2) and document a treatment plan to address the particular injury. Subsequently, 4DCT-based treatment plans will be compared with arthroscopic evaluation (obtained in Aim 2); any existing wrist x-rays (e.g. AP, lateral, stress views) and MRIs may be used in this comparison as well. The surgeon will then select and perform the targeted surgical intervention based on both 4DCT and arthroscopic findings. 4DCT will be performed, and the PRWE and VAS completed by patients at 1 year postoperatively; quantification of radioscapheocapitate contact patterns will be assessed during bilateral wrist flexion-extension and radial-ulnar deviation to determine if normal patterns of motion are restored.

(1a) This is a multisite study involving Mayo Clinic and non Mayo Clinic sites. *When checked, describe in detail the research procedures or activities that will be conducted by Mayo Clinic study staff.*

(1b) Mayo Clinic study staff will be engaged in research activity at a non Mayo Clinic site. *When checked, provide a detailed description of the activity that will be conducted by Mayo Clinic study staff.*

Subject Information

Target accrual: 60 subjects

Subject population (children, adults, groups):

Subjects with diagnosed symptomatic unilateral scapholunate instability for whom surgery is indicated, will be recruited.

Inclusion Criteria:

The following Inclusion criteria will apply to the patients with unilateral scapholunate instability. In the symptomatic wrist, they will have:

- 1) point tenderness over the dorsal aspect of the scapholunate joint, and one or more of the following:
- 2) positive Watson shift sign (Watson et al., J Hand Surg Am, 1988; 13:657-60);
- 3) suspected pathology on previous fluoroscopy or MRI

In the contralateral wrist, they will have an absence of scapholunate symptoms on physical exam.

Exclusion Criteria:

Exclusion criteria which will be applied to both wrists are as follows:

- 1) previously-diagnosed rheumatological conditions or connective tissue diseases;
- 2) inability to be appropriately positioned in the scanner for the imaging;
- 3) congenital malformations of the wrist or forearm;
- 4) diagnosed wrist osteoarthritis
- 5) age under 18 or over 60.

Research Activity

Check all that apply and complete the appropriate sections as instructed.

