Normalized volar/dorsal location of the gapping at the scapholunate joint for the 30 male and 30 female subjects obtained pre-surgically will be analyzed using the algorithm developed in Aim 1 to infer if and where any ligament injuries have occurred. Additionally, we will have findings on presence or absence of ligament injuries from volar and dorsal arthroscopy on each subject pre-surgically. Finally we will have PRWE and VAS data for each patient. The primary assessment will be of the percent of patients for whom the 4DCT and arthroscopic findings agree. Secondarily, we will fit models including PRWE and VAS to inform of thresholds for injury to see if this may improve prediction. These analyses will be repeated by sex, and other subgroups that may alter the relation between size and location of any gapping, and ligament injury, e.g. height, weight. In an exploratory manner, we will repeat analyses similar to Aim 1 to determine if the diagnostic model derived in Aim 1 might

be improved upon. With our sample of 60 patients, and the hypothesized agreement between the 4DCT of 95%, we will have 83% power to identify an agreement of 0.85 or less, using a chi-square test.

Aim 3:

Magnitude and direction of radioscapheoid contact center migration, bilaterally, will be analyzed during the 18 time steps during both radial-ulnar deviation and flexion-extension pre-surgically and 1-year post-surgically. Additionally, pre- and post-surgical PRWE and VAS will be analyzed. The change from pre- to post-surgical migration of the contact center in the injured limb as a percent normalization relative to the pre-surgical contralateral limb values will be determined and described using the t-distribution. Similarly, the change in pre- to post-surgical PRWE and VAS values will be compared. These analyses will be repeated by sex, and other subgroups that become apparent during the study. With our sample of 60 patients, and the hypothesized agreement between the 4DCT of 95%, we will have 83% power to identify an agreement of 0.85 or less, using a chi-square test. With a sample size of 60, using a two-sided size 0.05 t-test, we will have 80% power to detect an effect size of 0.37 for the analysis of quantitative outcomes.

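### As worded, the 83% power for 4DCT–arthroscopy agreement is power to detect a shortfall; no minimum agreement or alpha is stated for the conclusion that Hypotheses 2 and 3a need

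*Combined protocol and SAP*

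**What the plan says.** The Data Analysis Plan for Aim 2 sets the endpoint: "The primary assessment will be of the percent of patients for whom the 4DCT and arthroscopic findings agree". One sentence then gives the only test and power for it. It takes 60 patients and "the hypothesized agreement between the 4DCT of 95" per cent, and states "we will have 83% power to identify an agreement of 0.85 or less, using a chi-square test". The same sentence appears word for word in the Data Analysis Plan for Aim 3.

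No null value, minimum acceptable agreement, alpha, sidedness or confidence bound is attached to this test. The only alpha in the plan belongs to the quantitative outcomes in Aim 3: "using a two-sided size 0.05 t-test, we will have 80% power to detect an effect size of 0.37".

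The hypotheses are affirmative. Hypothesis 2 reads "The location of ligament injury can be predicted by the size and location of palmar or dorsal gapping at the scapholunate joint". Hypothesis 3a reads "Pre-operative treatment planning using 4DCT will provide equivalent findings as arthroscopic observations".

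The Aim 3 comparison is described in two ways. Specific Aim #3 sets 4DCT imaging findings against arthroscopy. Study Design and Methods, Aim 3, says "4DCT-based treatment plans will be compared with arthroscopic evaluation (obtained in Aim 2").

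**The concern.** A test whose rejection means that agreement is below 95% can show that 4DCT is inadequate. It cannot show that 4DCT is adequate. The best result it offers the hypotheses is non-significance, and with 60 patients that is compatible with agreement well below the level the plan itself singles out (0.85).

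At stake is the conclusion drawn from the primary assessment. The observed percent agreement is a valid estimate either way. But an analyst following the plan cannot tell whether success means not rejecting 0.95 (54/60 is enough), excluding 0.85 at one-sided 0.05 (56/60) or excluding 0.85 at two-sided 0.05 (57/60). Nothing in the plan prevents non-rejection from being reported as support.

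**Working it through.** **Inputs.** n = 60, one group with both assessments on each patient (Study Design and Methods, Aim 2: "4DCT scanning will be performed bilaterally on 60 patients (30 males, 30 females) with unilateral SLIL injury"). Agreement values 0.95 and 0.85, stated power 83%, chi-square test (Data Analysis Plan, Aim 2). Two-sided 0.05 is assumed for this test, borrowed from the t-test; one-sided 0.05 is the variant. All 60 patients are taken as evaluable.

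**Formula.** One-sample chi-square (score) test with null p0 and true value p1:
power = Φ[(|p1 − p0| − z·s0) / s1], where s0 = √(p0(1 − p0)/n) and s1 = √(p1(1 − p1)/n).
For 0.95, √(0.95 × 0.05/60) = 0.02814. For 0.85, √(0.85 × 0.15/60) = 0.04610.

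**1. The plan's figure, as worded (null 0.95, true 0.85).**
- Two-sided 0.05: (0.10 − 1.96 × 0.02814)/0.04610 = 0.973, so power is 83.5%. This reproduces the stated 83%.
- Exact: the test rejects at 53/60 or fewer (53/60 gives p = 0.018, 54/60 gives p = 0.076). P(X ≤ 53 | 0.95) = 0.030 and P(X ≤ 53 | 0.85) = 81.5%.
- One-sided 0.05 gives 87.8%, or 83.8% with a continuity correction.
- A two-group chi-square with 60 per group gives 44.6%, so it is not the source.

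**2. What non-rejection would mean.**
- If true agreement is 0.90, P(X ≥ 54) = 61%: the test fails to reject in most trials. At 0.85 it fails to reject in 18%.
- 54/60 is not rejected, yet its exact 95% CI is 0.795 to 0.962, which includes 0.85.
- There is no rejection region on the favourable side: 60/60 gives p = 0.076.

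**3. The direction the hypotheses need (null 0.85, true 0.95).**
- Two-sided 0.05: (0.10 − 1.96 × 0.04610)/0.02814 = 0.343, so power is 63.4%. Exact: success at 57/60 or more, upper-tail size 0.015, power 64.7%.
- One-sided 0.05: (0.10 − 1.645 × 0.04610)/0.02814 = 0.859, so power is 80.5%. Exact: success at 56/60 or more, size 0.042, power 82.0%.

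**4. Range over the minimum.** The plan names 0.85 only as the detectable value, so using it as the minimum is an assumption. Exact power at n = 60 and true agreement 0.95:

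| Minimum | Two-sided 0.05 | One-sided 0.05 |
|---|---|---|
| 0.80 | 92% (55/60 or more) | 97% (54/60 or more) |
| 0.85 | 65% (57/60 or more) | 82% (56/60 or more) |
| 0.90 | 19% (59/60 or more) | 19% (59/60 or more) |

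**5. Sensitivity to the hypothesised 95%.** With the 56/60 rule, power falls from 82% to 53% if true agreement is 0.925, and to 27% if it is 0.90.

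**The case against.** The strongest reply is that the sentence is only loosely written. The hypothesised 95% may be the expected true value, and 0.85 the level to be ruled out. On that reading the exact one-sided 0.05 power is 82.0%, one point from the stated 83% and as close as the 81.5% exact power of the literal reading. This stands: the number alone cannot settle the direction. Only the wording does, since it speaks of identifying agreement at or below 0.85. But the reversed reading needs a one-sided alpha and a minimum that the plan does not state.

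A second reply is that the study estimates a percentage without bias, so a confidence interval would meet most of the concern. That is fair as far as it goes. However, the plan names a test, uses it to justify n = 60, and specifies no interval for agreement.

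A reader might infer more than the documents support:
- That the test is certainly backwards, or the 83% wrong. The arithmetic is sound, and the direction is inferred.
- That the 60/60 result counts against the plan. Hypothesis 2 does not claim agreement above 95%; the relevant point is only that non-rejection of 0.95 does not establish adequacy.
- That Aim 3 reuses the sentence for a different outcome. Methods, Aim 3, points that way, but Specific Aim #3 describes a comparison close to that of Aim 2. The documents are inconsistent, and reuse is defensible under one of the two descriptions.
- That only Aim 3 lacks a definition. The Aim 2 analysis does not say either whether agreement means any injury, its location, or each part of the ligament.

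**Conclusion.** The concern holds in a limited form. As worded, and as the figure reproduces under an assumed two-sided 0.05, the stated power is for finding that 4DCT falls short of 95%. Hypotheses 2 and 3a need the opposite conclusion, and on every reading the plan lacks the minimum, alpha and sidedness for it.

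The size depends on choices the plan leaves open. With 0.85 as the minimum, true agreement 0.95 and 60 evaluable patients, the loss against the stated 83% is large at two-sided 0.05 (65%) and negligible at one-sided 0.05 (82%). If the reversed one-sided reading was intended, the repair is mainly to state it. The estimate of agreement is not affected. This should be fixed, with medium confidence because the direction rests on wording.

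**What to change.** Before the agreement data are analysed:

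1. Replace the chi-square test with an exact binomial test of H0: agreement ≤ a minimum stated by the sponsor.
2. State alpha and sidedness. The choice is the sponsor's. If the minimum is 0.85, two-sided 0.05 (the only alpha the plan uses elsewhere) means success at 57/60 or more, and the stated 83% must be lowered to 65%. One-sided 0.05 means success at 56/60 or more, with 82% power.
3. Report the matching bound: the two-sided 95% CI (0.861 to 0.990 at 57/60) or the one-sided 95% lower bound (0.854 at 56/60).
4. Define what counts as agreement, for Aim 2 as well as Aim 3.
5. Reconcile the two descriptions of the Aim 3 comparison before reusing the sentence there, and give Aim 3 its own stated minimum.

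The cost is SAP wording, two definitions and a restated power figure. The drawback is a less favourable power at two-sided 0.05, or up to 5% rather than 2.5% error toward success at one-sided 0.05. No extra patients are needed if one of these is accepted. Keeping 83% at two-sided 0.05 against 0.85 would take about 83 patients by normal approximation: [(1.96 × √0.1275 + 0.954 × √0.0475)/0.10]² = 82.4.
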